13.2.3 Exploratory objectives

Blood samples will be obtained at multiple time points (prior to vaccination, during, and post-vaccination) in order to procure PBMC for correlative studies. Functional studies will include ELISPOT, T cell poly-functionality by intra-cellular cytokine and degranulation analysis using multi-parametric flow cytometry, as detailed in Section 9.

Time to disease progression will be evaluated with physical examination and diagnostic imaging as clinically indicated. The time to disease progression will be described using Kaplan-Meier product limited method. The median progression-free survival (PFS), median overall survival (OS), and their 95% CIs will be estimated. The association between immunogenicity and PFS or OS will be explored by comparing the survival curves between immune responders versus non-responders. To determine whether the observed difference is larger than might be expected by chance, a permutation test will be used to compare the observed test statistic to the distribution of test statistics that would be seen if there were no difference between the two studies. Specifically, we will randomly shuffle the status of response and calculate the test statistic from the shuffled data. This procedure will be repeated 10,000 times and the resultant testing statistics will provide an accurate representation of the null distribution. The observed test statistics of between-study differences will be compared to the null distributions. For each outcome, the permuted p-value will be the fraction of permuted samples that resulted in a small statistic than the original sample [53].

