1.3 Exploratory objectives

Exploratory objectives include measurement of immune response, including the phenotype and functional status of neoantigen-specific T cells as measured by CYTOF analysis.

An exploratory clinical endpoint is to assess clinical response as measured by disease-free survival and overall survival.

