13.2 Data Analysis

As a phase I trial to evaluate the preliminary data on the safety and immunogenicity of a neoantigen peptide vaccine strategy, the data analysis for this study is descriptive in nature. Demographic and clinical characteristics of the sample, toxicity by grade, as well as response and time to toxicity will be listed and summarized using descriptive statistics.

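### The permutation p-value for immune response versus survival counts the wrong tail: for a statistic that grows with the difference it returns 1 minus the intended p-value

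*Combined protocol and SAP*

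**What the plan says.** Section 13.2.3 of the combined protocol and SAP explores the link between immunogenicity and PFS or OS by comparing survival curves of immune responders and non-responders. The aim is stated first: "To determine whether the observed difference is larger than might be expected by chance, a permutation test will be used". The mechanism follows: "we will randomly shuffle the status of response and calculate the test statistic from the shuffled data", repeated 10,000 times. The p-value for each outcome is then defined: "the permuted p-value will be the fraction of permuted samples that resulted in a small statistic than the original sample".

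The section does not say which statistic is computed, whether the test is one- or two-sided, or which group is coded 1. The nearest description is "The observed test statistics of between-study differences will be compared to the null distributions". The null hypothesis is also worded as "if there were no difference between the two studies", although this is one study and the shuffled label is response status.

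On the weight of this analysis, Section 1.3 says "An exploratory clinical endpoint is to assess clinical response as measured by disease-free survival and overall survival", and Section 13.2 says that "the data analysis for this study is descriptive in nature".

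**The concern.** The aim and the rule point to opposite tails. Asking whether a difference is larger than chance would produce means counting the shuffles that give a difference at least as large as the observed one. The rule counts the shuffles that give a smaller statistic. If the statistic increases with the separation of the curves, a large true difference yields a p-value near 1 and almost no difference yields a p-value near 0.

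This is the only test in the plan that links immune response to PFS or OS. Coded literally with an unsigned statistic, it would report widely separated curves as compatible with chance and nearly identical curves as strong evidence. Because statistic, sidedness and coding are all unstated, two analysts following the text could also report nearly opposite p-values from the same data.

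**Working it through.** The plan states no p-value, power or sample size for this test, so there is no figure of its own to reproduce.

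**Inputs from the plan**
- Number of shuffles: B = 10,000 (Section 13.2.3).
- Number of patients: 15 evaluable (Section 13.1.1).
- Test statistic, sidedness, group coding and alpha for this test: not given. The one-sided 0.05 in Section 13.1.3 belongs to the paired t-test for immunogenicity.

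**Assumed for illustration**, because the plan gives no responder rate: splits of 3/12, 5/10, 8/7 and 12/3 (responders/non-responders), all events observed, no tied times.

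**Step 1: the identity.** Let T be the observed statistic and T* a permuted one. Each shuffle falls either below T or at or above it, so

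#(T* < T)/B = 1 − #(T* ≥ T)/B.

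The left side is the written rule. The fraction on the right, #(T* ≥ T)/B, is the intended p-value when T grows with the difference. This needs no assumption about patients, hazard ratios or censoring.

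- Observed value above 9,900 of 10,000 shuffles: written rule 9,900/10,000 = 0.99; upper tail 100/10,000 = 0.01, or (1 + 100)/(10,000 + 1) = 0.0101.
- Observed value above only 100 shuffles: written rule 0.01; upper tail 0.99.

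**Step 2: exact log-rank enumeration at n = 15.** Order the patients by event time. With g = 1 for responders and p the proportion of responders among those still at risk at each event,

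Z = Σ(g − p) / √Σ p(1 − p), and chi-square = Z².

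Every possible allocation of response labels was enumerated. The observed allocation is full separation, with all responders progressing last.

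| Split | Allocations | Chi-square, upper tail | Chi-square, as written | Signed Z, responder = 1, as written | Signed Z, non-responder = 1, as written |
|---|---|---|---|---|---|
| 3/12 | 455 | 9/455 = 0.0198 | 0.980 | 0.000 | 0.998 |
| 5/10 | 3,003 | 7/3,003 = 0.0023 | 0.9977 | 0.000 | 0.9997 |
| 8/7 | 6,435 | 1/6,435 = 0.00016 | 0.9998 | 0.000 | 0.9998 |
| 12/3 | 455 | 1/455 = 0.0022 | 0.9978 | 0.000 | 0.9978 |

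**Step 3: the opposite extreme.** For the allocation with the smallest chi-square, all four splits give an upper-tail p of 1.00 and a written-rule p of 0.00. A signed Z under the written rule gives 0.45 to 0.55 with either coding.

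**Step 4: when the written rule works.** It gives a sensible one-sided p-value if the statistic is signed and becomes negative when responders do better (the responder = 1 column), or if the statistic is itself a p-value. The plan specifies neither. With the opposite coding of the signed statistic, the rule is reversed again.

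**The case against.** The strongest reply is that the sentence is a slip. As printed it is ungrammatical, and *smaller* is a repair by the reader, although the word *than* leaves little alternative. The aim sentence in the same paragraph shows which direction is of interest, and the curves will be inspected, so p = 0.99 beside clearly separated curves would probably be noticed. This lowers the practical risk but does not correct the rule. Changing *small* to *smaller* repairs the grammar and keeps the wrong tail. Changing it to *larger* still leaves the statistic, sidedness and ties undefined. If these are settled only after the survival data are seen, the test is no longer prespecified.

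Second, the reversal is conditional, since a signed statistic with one coding or a p-value used as the statistic would make the lower tail correct. That is true. But the plan states neither, and its wording about larger differences favours a statistic that grows with the difference.

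Third, the false-positive rate is not inflated. Under the null the observed statistic is equally likely to take any rank among the shuffles, so counting from either end rejects at about the nominal rate. This stands: what is lost is the ability to detect a real association, together with the meaning of any individual p-value.

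Fourth, full separation without censoring is an extreme illustration. That also stands, but the point rests on the identity in Step 1, not on the example.

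**Conclusion.** The p-value rule is wrong as written, with low impact. For any statistic that grows with the difference between responders and non-responders, it returns 1 minus the upper-tail p-value, and this holds without assumptions. In the exact illustrations, full separation is reported as 0.980 to 0.9998 where the upper tail is 0.020 to 0.00016; those figures rest on the assumed splits, no censoring and no ties. The conclusion takes *small* as *smaller* and assumes that the unnamed statistic is unsigned; for a signed statistic, the result depends on a coding that the plan does not give.

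The effect is confined to the exploratory association p-values for PFS and OS. Primary and secondary analyses, sample size and stopping rules are untouched. It should still be fixed, because it is the plan's only test of that association and the correction is simple.

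**What to change.** In Section 13.2.3:

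1. Name the statistic and its sidedness, for example a two-sided log-rank chi-square.
2. Define p as the fraction of permuted statistics at least as extreme as the observed one in that direction. For a chi-square this means greater than or equal to the observed value, computed as (1 + count)/(10,000 + 1). Full enumeration is an alternative: at n = 15 the splits examined have at most 6,435 allocations, fewer than the planned 10,000 shuffles.
3. Editorially, replace the references to two studies and to between-study differences with responders and non-responders.

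The cost is about two sentences of analysis text, with no effect on data collection, sample size or conduct.

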14 DATA MANAGEMENT

Data collected will be collected using paper case report forms or OnCore electronic data capture forms. Forms must be completed within 28 days of time point.

Case report forms with appropriate source documentation will be completed according to the schedule listed in this section.

Case Report Form	Submission Schedule
Original Consent Form	Prior to registration
Registration Form Eligibility Form Demographics Form On-Study Form Medical History Form	Prior to starting treatment
Physical Exam Form	Enrollment Mid chemo End of chemo Day 1 Day 4 Day 8 Day 15 Day 22 Day 50 Day 78 4 weeks after last injection 1 year after last injection
Vaccine Administration Form	Day 1 Day 4 Day 8 Day 15 Day 22 Day 50 Day 78
Immune Monitoring Form	Enrollment Mid chemo End of chemo Day 1 Day 22 Day 50 Day 78
Imaging Form	Mid chemo End of chemo
Toxicity Form	Day 1 Day 4 Day 8 Day 15 Day 22 Day 50 Day 78
Concomitant Medications Form	Continuous through Week 25
Follow Up Form	4 weeks after last injection 1 year after last injection Year 2 and annually thereafter
Death Form	Time of death
Progression Form	Time of disease progression
MedWatch Form	See Section 11.0 for reporting requirements

Any queries generated by Washington University must be responded to within 28 days of receipt by the participating site. The Washington University research team will conduct a regular review of data status at all secondary sites, with appropriate corrective action to be requested as needed.

14.1 Adverse Event Collection in the Case Report Forms

All adverse events that occur beginning with start of treatment (minus exceptions defined in Section 11.0) must be captured in the Toxicity Form. Baseline AEs should be captured on the Medical History Form.

Participant death due to disease progression should be reported on the Toxicity Form as grade 5 disease progression. If death is due to an AE (e.g. cardiac disorders: cardiac arrest), report as a grade 5 event under that AE. Participant death must also be recorded on the Death Form.

15 AUDITING

As coordinating center of this trial, Washington University (via the Quality Assurance and Safety Monitoring Committee (QASMC)) will monitor each participating site to ensure that all protocol requirements are being met; that applicable federal regulations are being followed; and that best practices for patient safety and data collection are being followed per protocol. Participating sites will be asked to send copies of all audit materials, including source documentation. The audit notification will be sent to the Washington University Research Patient Coordinator, who will obtain the audit materials from the participating institution.

Notification of an upcoming audit will be sent to the research team one month ahead of the audit. Once accrual numbers are confirmed, and approximately 30 days prior to the audit, a list of the cases selected for review (up to 10 for each site) will be sent to the research team. However, if during the audit the need arises to review cases not initially selected, the research team will be asked to provide the additional charts within two working days.

Items to be evaluated include:

- Subject screening and enrollment
- Reporting of adverse events
- Maintenance of HIPAA compliance
- Completeness of regulatory documentation
- Completeness of participant documentation
- Acquisition of informed consent
- IRB documentation
- Issues of protocol adherence

Additional details regarding the auditing policies and procedures can be found at

<https://siteman.wustl.edu/wp-content/uploads/2015/10/QASMC-Policies-and-Procedures-03.31.2015.pdf>

16 MULTICENTER REGULATORY REQUIREMENTS

Washington University requires that each participating site sends its informed consent document to be reviewed and approved by the Washington University Regulatory Coordinator (or designee) prior to IRB/IEC submission.

Site activation is defined as when the secondary site has received official written documentation from the coordinating center that the site has been approved to begin enrollment. At a minimum, each participating institution must have the following documents on file at Washington University prior to study activation:

- Documentation of IRB approval of the study in the form of a letter or other official document from the participating institution's IRB. This documentation must show which version of the protocol was approved by the IRB.
- Documentation of IRB approval of an informed consent form. The consent must include a statement that data will be shared with Washington University, including the Quality Assurance and Safety Monitoring Committee (QASMC), the DSMB (if applicable), and the Washington University study team.
- Documentation of FWA, signed FDA Form 1572 (if applicable), and the CVs of all participating investigators.
- Protocol signature page signed and dated by the investigator at each participating site.

The coordinating center Principal Investigator (or designee) is responsible for disseminating to the participating sites all study updates, amendments, reportable adverse events, etc. Protocol/consent modifications and IB updates will be forwarded electronically to the secondary sites within 4 weeks of obtaining Washington University IRB approval. Activated secondary sites are expected to submit protocol/consent/IB modifications to their local IRBs within 4 weeks of receipt unless otherwise noted. Upon the secondary sites obtaining local IRB approval, documentation of such shall be sent to the Washington University study team within 2 weeks of receipt of approval.

Documentation of participating sites' IRB approval of annual continuing reviews, protocol amendments or revisions, all SAE reports, and all protocol violations/deviations/exceptions must be kept on file at Washington University.

The investigator or a designee from each institution must participate in a regular conference call to update and inform regarding the progress of the trial.

17 REGULATORY AND ETHICAL OBLIGATIONS

17.1 Informed consent

In accordance with US FDA regulations (21 CFR 50) and guidelines (Federal Register, May 9, 1997, Vol. 62, Number 90 - ICH Good Clinical Practice Consolidated Guideline) it is the investigator's responsibility to ensure that witnessed informed consent is obtained from the subject before participating in an investigational study, after an adequate explanation of the purpose, methods, risks, potential benefits and subject responsibilities of the study. Procedures that are to be performed as part of the practice of medicine and which would be done whether or not study entry was contemplated, such as for diagnosis or treatment of a disease or medical condition, may be performed and the results subsequently used for determining study eligibility without first obtaining consent. On the other hand, informed consent must be obtained prior to initiation of any screening procedures that are performed solely for the purpose of determining eligibility for research.

Each subject must be given a copy of the informed consent. The original signed consent must be retained in the institution's records and is subject to review by the sponsor, the HRPO and any other applicable regulatory agencies responsible for the conduct of the institution. All elements listed in the ICH Good Clinical Practice guidelines must be included in the informed consent.

Informed consent will be obtained by either the principal investigator or by individuals approved by the principal investigator and whose names have been submitted to the IRB. Informed consent will be obtained from the subject after the details of the protocol have been reviewed. The individual responsible for obtaining consent will assure, prior to signing of the informed consent, that the subject has had all questions regarding therapy and the protocol answered.

17.2 Institutional Review Board

In accordance with US FDA regulations (21 CFR 56) and guidelines (Federal Register, May 9, 1997 Vol. 62 Number 90 - ICH Good Clinical Practice Consolidated Guideline) all research involving human subjects must be reviewed and approved by the local IRB. All modifications to the protocol, consent forms, or other study documents must be reviewed and approved by the local IRB. At Washington University School of Medicine, the Human Research Protection Office serves as the local IRB.

17.3 Subject confidentiality

In order to ensure subject confidentiality, each subject will be assigned a study number. Subject samples and medical information will be de-identified and labeled with the study number. The link between subject identification and study number will be safeguarded in a secure file in a locked room, and access will be restricted to the principal investigator, study coordinator, and other co-investigators as necessary.

Collected data will be recorded on case report forms. Case report forms will be safeguarded in a locked cabinet and/or a password-protected secure computer drive and access will be restricted to the principal investigator, study coordinator, and other co-investigators as necessary. Subject medical information related to, or obtained for the purposes of this trial are confidential, and disclosure to third parties is prohibited. The exception is regulatory authorities including the FDA, NIH/OBA, and the local IRB. Data from this study must be available for inspection on request of regulatory authorities including the FDA and the local IRB.

18 ADMINISTRATIVE AND LEGAL OBLIGATIONS

18.1 Study documentation and retention of records

18.1.1 Study documentation

Source documents are original documents, data, and records from which the subject's data are obtained. These include but are not limited to hospital records, clinical and office charts, laboratory and pharmacy records, diaries, diagnostic imaging studies, and correspondence.

The principal investigator and staff are responsible for maintaining a comprehensive file of all study-related documents, suitable for inspection at any time by representatives from the PRMC, HRPO, FDA, and any other applicable regulatory agency.

Pertinent documents in the study file include:

- (1) The original protocol with all amendments
- (2) Curriculum vitae of principal investigator and co-investigators
- (3) Approval notification and any other correspondence with the PRMC, HRPO, NIH RAC and FDA

Pertinent documents in each individual subject file include:

- (1) Informed consent forms
- (2) Case report forms
- (3) Supporting copies of source documentation

All original source documentation must be readily available.

18.1.2 Retention of records

The principal investigator must retain records related to this study including protocols; amendments; IRB/IBC approvals; FDA IND records and other correspondence; completed, signed and dated consent forms; patient medical records; case report forms; drug accountability records and any other correspondence related to the conduct of the study.

U.S. FDA regulations (21 CFR 312.62[c]) require that all records pertaining to the conduct of this study, must be retained by the responsible investigator for a minimum of 2 years after marketing application approval. If no application is filed, these records must be kept 3 years after the investigation is discontinued and the U.S. FDA and the applicable local health authorities are notified.

18.2 Policy regarding research-related injuries

Washington University School of Medicine investigators and their staffs will try to reduce, control, and treat any complications from this research.

Any subjects who believe that they have been injured as a result of participation in this study will be instructed to contact the principal investigator, [name]. at [contact]. Alternatively, they can contact [name], Chair of the Human Research Protection Office, at [contact].

Decisions about payment for medical treatment for research-related injuries will be made by Washington University School of Medicine.

In general, Washington University School of Medicine will provide no long-term medical care or financial compensation for research-related injuries.

18.3 Study termination

The principal investigator and the Siteman Cancer Center reserve the right to terminate the study. The principal investigator will notify the PRMC and HRPO in writing of the study's completion or early termination.

20 APPENDICES

20.1 Abbreviations

AE	Adverse Event
CBER	Center for Biologics Evaluation and Research
CFR	Code of Federal Regulations
CPA	Cooperative Project Assurance
CR	Complete response
CRA	Clinical Research Associate
CRF	Case Report Form
CT	Computed Tomography
CTCAE	Common Terminology Criteria for Adverse Events
CTEP	Cancer Therapy Evaluation Program
DNA	Deoxyribonucleic acid
DCTD	Division of Cancer Treatment and Diagnosis
ELISPOT	Enzyme-linked immunospot assay
ECOG	Eastern Cooperative Oncology Group
FDA	Food and Drug Administration
FWA	Federal-wide Assurance
GLP	Good Laboratory Practice
GMP	Good Manufacturing Practice
GPC	Gel permeation chromatography
HIPAA	Health Insurance Portability and Accountability Act
HLA	Human leukocyte antigen
HRPO	Human Research Protection Office (Institutional Review Board at WUSM)
IBC	Institutional Biosafety Committee
ICH	International Conference of Harmonization
IDB	Investigational Drug Branch
IRB	Institutional Review Board
LD	Longest diameter
MPA	Multiple Project Assurance
MRI	Magnetic Resonance Imaging
NCI	National Cancer Institute
NIH	National Institutes of Health
OBA	Office of Biotechnology Activities
OHRP	Office for Human Research Protection
PBMC	Peripheral blood mononuclear cell
PD	Progressive disease
PHI	Protected Health Information
PR	Partial response
RAC	Recombinant DNA Advisory Committee
RECIST	Response Evaluation Criteria in Solid Tumors
QASMC	Quality Assurance and Safety Monitoring Committee
SAE	Serious Adverse Event
SAS	Statistical Analysis System; Analytical software from the SAS Institute, Cary, NC
SCC	Siteman Cancer Center
SCIP	Siteman Cancer Information Portal
SD	Stable disease
SD	Standard Deviation
THF	Tetrahydrofuran
UPN	Universal Product Number
WUSM	Washington University School of Medicine
WUSTL	Washington University in Saint Louis

